**Abbreviations glossary**

LBP	Low Back Pain
AOT	Action Observation Training
ODI-I	Oswestry Disability Index
NRS	Numeric Rating Scale
SF36	Medical Outcomes Study Short Form 36
TSK	Tampa Scale of Kinesiophobia

## 1 Synopsis

**Title** Action Observation Training in patients with chronic low back pain

### **Introduction and rational**

Low back pain (LBP) represents the pathology of the musculoskeletal system with greater prevalence in adults and it is one of the main causes of disability. Structural and functional brain modifications have been described in patients with chronic pain in the musculoskeletal system. In these patients, the central nervous system can therefore be considered one of the target structures of the treatment. The Action Observation Training (AOT) represents an effective rehabilitative approach to enhance the motor function in both central nervous system and musculoskeletal pathologies. So far no study has investigated the effects of AOT in patients with chronic LBP. The study aims to determine the efficacy of an AOT treatment in patients with chronic LBP.

### **Population and patients recruitment criteria**

N. 50 aspecific chronic LBP diagnosed patients will be sorted (duration of the symptoms over 12 weeks). The inclusion criteria will be: understanding of Italian language and an age over 65 years. Patients with severe sight and/or hearing impairment and with cognitive deficit (Mini Mental State Examination  $\leq 21$ ) will be excluded. Subjects with specific etiology LBP or who have previously undergone AOT will be excluded too.

### **Design and study duration**

The study is a single-blind controlled randomized clinic trial.

### **Outcomes**

The primary outcome will be the evaluation of the disability through a Oswestry Disability Index questionnaire. The secondary outcomes will be the rating of the pain (Numeric Rating Scale), the quality of life (Short-Form 36) and the fear of movement (Tampa Scale of Kinesiophobia). The outcome measures will be taken before the treatment (T0), after three weeks (T1) and four months upon the end of the treatment (T2). At T0 the subjects' attention skill will be evaluated.

**Statistical methods and data analysis**

Upon data collection the normality and homogeneity of the demographic variables and of the outcome measures to the baseline will be evaluated. Possible differences after treatment, inter-group, intragroup will be investigated through ANOVA test for repeated measurements including any possible post hoc analysis.

**Ethical considerations**

The subject study is aimed to determine the efficacy of an AOT treatment in patients affected by chronic LBP, by treating the participants with an intervention and evaluation as it was described in literature. They showed no evidence of adverse events for the health. The materials used for the study will be provided by the Physiotherapy Dept. of Humanitas Clinical Institute. The treatments will last 30 minutes while the evaluation will last 15 minutes.

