### **6.1 General design**

The patients will be recruited and then randomly assigned by an external collaborator (allocation concealment) to the experimental group or to a control group. The patients belonging to the experimental group will be asked to watch a video showing a person carrying out some exercises (12 exercises: 3 stretching exercises, 3 core stability exercises, 3 mobilization exercises and 3 functional exercises) and later on they will be asked to repeat them. The observation of the exercise and its performance will last 8 minutes (4 minutes for observation and 4 minutes to repeat them). On the other hand, the patients belonging to the control group will be given a brochure with the same exercises the patients of the experimental group received through the video. They will be asked to read the exercise 3 times and to carry it out for 4 minutes. Both groups will have to watch the video or read the brochure and repeat the exercises 5 times per week for 3 weeks. They will be

provided with a diary to write daily notes about the performance of the exercises (day and time of the performance, possible problems, etc).

The patients will be evaluated before the treatment (T0), three weeks upon its beginning (T1) and 4 months upon the end of it (T2). The evaluation will consist in the administration of the Oswestry Disability Index, of the Tampa Scale of Kinesiophobia, of the Numerical Rating Scale and of the Medical Outcomes Study Short Form 36. At T0 the subjects' attention skill will be evaluated through the Brief Cognitive Assessment Tool [16]

A physiotherapist will instruct the patients about the exercises to repeat while a second blinded physiotherapist about the group the patients belong to, will administer the evaluation scales.

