## **7 Statistical considerations**

### **7.1 Sample size**

The Oswestry Disability Index represents the primary outcome measure. The sample size has been calculated considering an MCID of 12.8 points among the general population with a 14 point standard deviation. Assuming a 80% power and a probability to refuse the null hypothesis when true (alpha error) of 5%, 25 patients per group will be recruited.

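### Does the 30-minute treatment time in the Synopsis contradict the 8 minutes in Section 6.1 so that the treatment under test is undefined?

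*Combined protocol and SAP*

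**What the plan says.** The Synopsis, under Ethical considerations, gives one treatment time beside the evaluation time: "The treatments will last 30 minutes while the evaluation will last 15 minutes". It does not say whether this is a home session, a session with the physiotherapist, or the same for both arms.

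Section 6.1 describes the content. The experimental arm watches and then repeats a set given as "12 exercises: 3 stretching exercises, 3 core stability exercises, 3 mobilization exercises and 3 functional exercises". The timing is "The observation of the exercise and its performance will last 8 minutes (4 minutes for observation and 4 minutes to repeat them". The control arm has the same exercises in a brochure: "They will be asked to read the exercise 3 times and to carry it out for 4 minutes". The frequency is common to both arms: "Both groups will have to watch the video or read the brochure and repeat the exercises 5 times per week for 3 weeks".

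Section 6.1 gives no total session time and no number of exercises per session, and does not mention 30 minutes. For the study scheme, Sections 6 and 15 refer to Enclosure A, which is not part of the text under review.

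**The concern.** Read side by side, the two places seem to give different lengths for the same thing, 30 minutes and 8 minutes, and a list of 12 exercises fits neither easily. The timing sentence in Section 6.1 also moves from the singular to the plural, so the unit of the 8 minutes is open.

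The trial compares two ways of delivering the same exercises. If exercise time differed between arms because staff worked from different passages, a difference in the Oswestry Disability Index could partly reflect the amount of exercise rather than action observation. Within arms, uneven exercise time would add noise. The burden stated for patients over 65 could also be too low. The control arm's three readings have no stated length, so the 30 minutes cannot be checked for that arm at all.

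**Working it through.** **Inputs.** Treatment time 30 minutes (Synopsis, Ethical considerations). Observation 4 minutes plus performance 4 minutes; 12 exercises; control performance 4 minutes after three readings; 5 times per week for 3 weeks (all Section 6.1). Sessions: 5 × 3 = 15.

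**Step 1: can the 30 minutes be reproduced?** If the 8 minutes is per exercise and k exercises are done per session, session time = 8 × k.

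| Reading of Section 6.1 | Minutes per session | Minutes over 15 sessions |
|---|---|---|
| 8 minutes is the whole session | 8 | 120 |
| per exercise, k = 3 | 24 | 360 |
| per exercise, k = 4 | 32 | 480 |
| per exercise, k = 12 | 96 | 1,440 |
| Synopsis figure | 30 | 450 |

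Since 30 / 8 = 3.75, no whole number of exercises gives exactly 30. Four give 32, close to a rounded 30. The documents state no value of k, so 30 is neither reproduced nor ruled out.

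**Step 2: how wide is the uncertainty?** The extremes differ by 1,440 / 120 = 12. Each end is strained.
- The low end, with all 12 exercises done, leaves 4 × 60 / 12 = 20 seconds of observation and 20 seconds of performance per exercise. It also sits badly with the control-arm sentence, which is singular throughout.
- The high end assumes all 12 exercises in every session, which Section 6.1 does not say, and it exceeds the only stated treatment time by 96 / 30 = 3.2 times.

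The factor of 12 describes what the wording permits. It does not estimate the spread of treatment given.

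**Step 3: does the ambiguity reach the comparison?** Planned performance time over the programme, with the same reading in both arms:
- 4 minutes per session: 4 × 15 = 60 minutes in each arm.
- 4 minutes per exercise, k exercises: 4 × k × 15 = 60k minutes in each arm, so 240 for k = 4 and 720 for k = 12.

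The between-arm difference is 0 in every row. What differs is watching (timed) against reading (three times, untimed), and that is the contrast being tested.

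**Step 4: does session length enter the statistics?** Section 7.1 uses a difference of 12.8 points, a standard deviation of 14, 80% power and 5% alpha. A two-sided t-test needs 20 per group, and the planned 25 give power of about 0.89. None of these inputs involves session length, and neither does the repeated-measures ANOVA in Section 7.2.

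**The case for a change.** The strongest case for acting is that a reader must invent a subset of exercises to make the two passages agree, and that alone shows the amount of treatment is not written down. The trial could not be replicated from this text. The diary may not recover what was done: Section 6.1 names the day, the time and any problems, but not minutes or number of exercises. On the 96-minute reading the burden is understated about threefold. The remedy would cost only wording.

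Most of this stands as a remark on reporting. The unit and the number per session are missing, and the two passages must be reconciled.

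What does not stand is the step from there to a biased comparison. It requires the two arms to work from different readings. Patients receive a video or a brochure, not the protocol. The exercises are the same, and Section 6.1 describes one physiotherapist role giving instruction. Nothing suggests that staff would take one arm's timing from the Synopsis and the other's from Section 6.1. The burden point depends on the 96-minute reading, and the patient information was not available to check it. Enclosure A might also contain the schedule.

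**Conclusion.** This is a gap in the description of the intervention, and the plan does not need to change because of it. The 30 minutes cannot be derived from Section 6.1 (8, 24, 32 or 96 minutes, depending on unit and number). The text leans towards a per-exercise unit, under which an unstated subset of about four would roughly match, so a contradiction is not proven. The team cannot make the video and brochure without settling both numbers. Reconciling the passages is then a clerical step, with values that belong to the clinical team; none is proposed here.

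Under any single reading, planned performance time is identical between arms, and the sample size, type I error and analysis are untouched. This conclusion assumes that one reading is applied to both arms, which the shared exercises, frequency and performance time in Section 6.1 support. Evidence that the arms were instructed to different timings would reopen the point.

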**Timing of the study**

Patients recruiting: May 2019  
Data analysis: July 2020  
Report submitted: September 2020

## **2 Background and introduction**

The Low Back Pain (LBP) represents the pathology of the musculoskeletal system with greater prevalence in adults (with a 18.6% to 57.4% variable index) [1]. It is one of the main causes of disability with a high rate of chronicity and absenteeism from work [1] [2] [3]. The clinical course of the LBP is highly variable and from 3 to 10% of the affected patients develops a chronic pain (more than 3 months lasting).

Different kinds of interventions have been proposed to handle this pathology (including different types of pharmacological and chirurgical approaches); they have achieved contrasting and sometimes not satisfactory results [4]. The treatment of the LBP traditionally focuses on what is defined as “end organ dysfunction”, criteria according to which the symptom experienced by the patient derives from structural or functional anomalies of the musculoskeletal system. Hence the intervention aims to normalize the peripheral deficit through techniques such as stretching, anesthesia or denervation but with scarcely important results [5].

Parallely, many studies have described structural and functional cerebral modifications in patients with musculoskeletal system chronic pain; these modifications would have a key role in the development and in the continuation of a state of pain which persists over time [5] [6]. The central nervous system can therefore be considered one of the target structures of the treatment of patients affected by chronical LBP, thus developing approaches such as the Action Observation Training (AOT) [7]. It consists in asking the patient to meet some tasks in order to recruit the same neural substrates involved while carrying out those tasks [8] The efficacy of this approach has been proven by the improvement of the motor function and the functional and structural brain plasticity [9] [10].

## **3 Study rational**

So far there have not been studies which investigated the effects of AOT in patients with chronic LBP. The AOT enables to activate specific areas of the cerebral cortex, strengthening some networks and facilitating the activation of the ones which have been damaged due to a neurological damage, pain or immobilization [7]. Functional and structural plastic modifications of the central neurological system are subtended to the use of AOT. This approach could therefore give positive results in patients with chronic LBP, pathology in which the functional and structural cerebral alterations have been described.

## **4 Study outcomes**

### **4.1 General outcomes**

The outcome of the study is to determine the efficacy of the Action Observation Training in the treatment of chronical LBP affected patients.

### **4.2 End-points**

#### ***4.2.1 Primary Endpoint***

The primary outcome will be to evaluate the disability through the Oswestry Disability Index (ODI-I). This is a specific pathology questionnaire, it is self-administered and validated in Italian [11]. It is made of ten items about everyday activities. The scores will be interpreted as described by

Fairbank [12]: 0-20% is considered minimum disability, 21-40% modest disability, 41-60% severe disability, 61-80% serious disability and 81-100% total disability [13].

#### **4.2.2 Secondary Endpoint**

The secondary endpoints will consist in the evaluation of the pain, of the quality of life and of the fear of movement. The pain will be examined through the Numeric Rating Scale (NRS); it consists in a 10 cm segment numbered from 0 to 10, through which the subject will have to rate his/her perception of the pain (0 corresponds to “no pain”, while 10 to “maximum pain”). The quality of life will be evaluated through the Medical Outcomes Study Short Form 36 (SF36), while the fear of movement through the Tampa Scale of Kinesiophobia (TSK).

## **5 Criteria for the recruitment of the patients**

### **5.1 Inclusion criteria**

- Patients with chronic aspecific LBP (documented story of more than 12 week-long symptomatology)
- Good understanding of Italian language
- Aged over 65

### **5.2 Exclusion criteria**

- Severe sight or hearing impairment
- Cognitive deficit (objectified by a Mini Mental State Examination score  $\leq 21$  [14]).
- Specific LBP (previous spine surgery, deformation, infection, fracture, malignant tumor, general disorders or neuromuscular pathologies)
- Patients who previously underwent AOT

As confirmation of the eligibility of the subjects in the study the following will be used: their clinical history, x-rays of the lumbar spine and in particularly uncertain cases, the computed tomography or the nuclear magnetic resonance. Common degenerative modifications such as the degeneration of the disc or the spondyloarthrosis will not be considered as exclusion criteria [15].

## **6 Study design**

The study is a single-blind controlled randomized clinic trial. See Enclosure A

### **6.1 General design**

The patients will be recruited and then randomly assigned by an external collaborator (allocation concealment) to the experimental group or to a control group. The patients belonging to the experimental group will be asked to watch a video showing a person carrying out some exercises (12 exercises: 3 stretching exercises, 3 core stability exercises, 3 mobilization exercises and 3 functional exercises) and later on they will be asked to repeat them. The observation of the exercise and its performance will last 8 minutes (4 minutes for observation and 4 minutes to repeat them). On the other hand, the patients belonging to the control group will be given a brochure with the same exercises the patients of the experimental group received through the video. They will be asked to read the exercise 3 times and to carry it out for 4 minutes. Both groups will have to watch the video or read the brochure and repeat the exercises 5 times per week for 3 weeks. They will be

provided with a diary to write daily notes about the performance of the exercises (day and time of the performance, possible problems, etc).

The patients will be evaluated before the treatment (T0), three weeks upon its beginning (T1) and 4 months upon the end of it (T2). The evaluation will consist in the administration of the Oswestry Disability Index, of the Tampa Scale of Kinesiophobia, of the Numerical Rating Scale and of the Medical Outcomes Study Short Form 36. At T0 the subjects' attention skill will be evaluated through the Brief Cognitive Assessment Tool [16]

A physiotherapist will instruct the patients about the exercises to repeat while a second blinded physiotherapist about the group the patients belong to, will administer the evaluation scales.

## **7 Statistical considerations**

### **7.1 Sample size**

The Oswestry Disability Index represents the primary outcome measure. The sample size has been calculated considering an MCID of 12.8 points among the general population with a 14 point standard deviation. Assuming a 80% power and a probability to refuse the null hypothesis when true (alpha error) of 5%, 25 patients per group will be recruited.

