### **7.2 Analysis**

The statistical analysis will be carried out upon the data collection through SPSS 20.0. software. The categorical variables will be described in terms of proportion, while the continuous variables in terms of average and standard deviation or median and interquartile range. The normal intake of the demographic variables and of the outcome measures will follow through the Kolmogorov-Smirnov. The possible post intervention inter-group and intra-group differences relative to the continuous outcome measures will be evaluated through the ANOVA test for repeated measurements and an eventual post hoc analysis will be carried out later. The threshold value of the level of significance will be set at 0.05.

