## **8 Study abandonment**

The patients who during or at the end of each scheduled evaluations set by the protocol will abandon the study will be immediately excluded from it. The patients will be informed about the possibility to quit the study also during the follow-up periods, after informing any experimenter. The acquisitions which have not been completed by the patients will be excluded from the analysis of the results.

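### Section 7.1's inputs do not reproduce 25 per group, and no visible passage names the visit or ANOVA term to which the 80% power belongs

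*Combined protocol and SAP*

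**What the plan says.** - **Sample size (7.1).** The number was reached "considering an MCID of 12.8 points among the general population with a 14 point standard deviation". The next sentence reads "Assuming a 80% power and a probability to refuse the null hypothesis when true (alpha error) of 5%, 25 patients per group", and its closing words say that these patients will be recruited. The section names no test, sidedness, visit or loss allowance. It does not say whether 14 is the SD of the score or of the change.
- **Analysis (7.2).** Post-intervention "inter-group and intra-group differences relative to the continuous outcome measures will be evaluated through the ANOVA test for repeated measurements", with a post hoc analysis if needed, at a threshold of 0.05. The synopsis, under statistical methods, says that differences after treatment "will be investigated through ANOVA test for repeated measurements including any possible post hoc analysis".
- **Primary outcome.** In the synopsis: "The primary outcome will be the evaluation of the disability through a Oswestry Disability Index questionnaire". Section 4.2.1 likewise names the instrument, without a visit or contrast.
- **Visits (6.1).** T0 is before treatment, T1 three weeks after its start, and T2 four months after its end. Neither T1 nor T2 is given priority.
- **Incomplete data (8).** "The acquisitions which have not been completed by the patients will be excluded from the analysis of the results". No expected loss is given.

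**The concern.** A reader who puts 7.1's four inputs into the usual two-group formula does not get 25, and the section gives nothing that closes the gap. That alone is minor. What matters more is that the 80% cannot be attached to any test in 7.2. A repeated-measures ANOVA with two groups and three visits yields a group effect, a time effect and a group-by-time interaction, and post hoc contrasts may follow. These answer different questions and have different power. T1 falls at the end of treatment and T2 four months later, so the choice of visit also changes what the trial claims. If the deciding line is not fixed before the data are seen, nobody can check that the trial is adequately sized for it or say in advance what result would count as success.

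**Working it through.** **Step 1: the plan's own figure.** Inputs from 7.1: difference 12.8, SD 14, power 80%, alpha 5%. Assumed: two independent groups of equal size, t-test at one visit.

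Normal approximation, two-sided: n = 2 × (1.960 + 0.842)² × (14/12.8)² = 18.8, so 19 per group.

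Exact t-test, noncentrality (12.8/14) × √(n/2), df = 2n − 2:

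| n per group | two-sided 5% | one-sided 5% |
|---|---|---|
| 15 | 67.6% | 78.8% |
| 16 | 70.6% | 81.1% |
| 19 | 78.3% | 86.9% |
| 20 | 80.4% | 88.4% |
| 25 | 88.6% | 93.8% |

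The inputs give 20 per group two-sided or 16 one-sided. Neither gives 25.

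**Step 2: what would give 25.** Each route needs something that 7.1 does not state:
- a 20% loss: 20/(1 − 0.20) = 25;
- an SD of 15.8 with a difference of 12.8;
- a difference of 11.3 with an SD of 14;
- a group-by-time test with correlation 0.3 between visits (step 3), which has 78.2% power at 24 and 80.0% at 25.

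**Step 3: power by deciding term.** Assumptions not in the documents: SD 14 at each visit, compound symmetry, a difference of 0 at T0 and 12.8 at both T1 and T2, correlation r = 0.3/0.5/0.7, two-sided 5%.

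- *Group-by-time.* The mean difference over visits is 8.53, and the squared deviations sum to 8.53² + 4.27² + 4.27² = 109.2. λ = (n/2) × 109.2/(196 × (1 − r)), F with 2 and 2(2n − 2) df. At n = 25, λ = 9.95/13.93/23.22.
- *Group effect over T1 and T2 only.* Difference 12.8, SD 14 × √((1 + r)/2) = 11.29/12.12/12.91.
- *Group effect averaging in T0.* Difference 12.8 × 2/3 = 8.53, SD 14 × √((1 + 2r)/3) = 10.22/11.43/12.52.
- *ANCOVA at one visit, adjusted for T0.* Difference 12.8, residual SD 14 × √(1 − r²) = 13.36/12.12/10.00, df 2n − 3.

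| Deciding test | 25 per group (r = 0.3/0.5/0.7) | 20 per group |
|---|---|---|
| Group-by-time | 80/92/99% | 70/84/97% |
| Group effect, T1 and T2 only | 97.5/95.5/93.0% | 94/90/86% |
| Group effect averaging in T0 | 82/73/66% | 73/63/56% |
| ANCOVA at one visit | 91/95/99% | 84/90/98% |

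The 20 per group column illustrates a 20% loss; the documents give no rate.

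**Step 4: if 14 is the SD of change.** The ANCOVA residual SD becomes 14 × √((1 + r)/2). Power is then 97.5/95.5/93.0% at 25 and 93.7/90.2/86.3% at 20.

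**The case against.** The strongest reply is that nothing in 7.1 has been shown to be miscalculated. The section names no t-test. It speaks of patients to be recruited, not patients evaluable, and 20 inflated for a 20% loss is exactly 25. Group-by-time at a correlation of 0.3 also first reaches 80% at 25. On the t-test the excess is in the safe direction. All of this stands, and for these reasons a reader who infers an arithmetic error goes further than the text allows. What remains is that none of these routes is written down.

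A reader might also infer from the 66% and 73% figures that the planned ANOVA is underpowered. The documents do not support that. Those figures belong to a group effect that averages in T0. Both 7.2 and the synopsis speak of differences arising after treatment, and that wording does not favour such a term. A group effect over T1 and T2 alone has at least 93% power under the same assumptions. Nor does any passage say that either of two terms may count as success, so no inflated false-positive rate can be charged to the plan.

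Two limits apply. Enclosure A, the study scheme, is not reproduced and could name a primary visit. A visit alone would still leave the ANOVA term open, and the sections that should name the term do not. The correlations in step 3 are assumed, but the failure to reproduce 25 and the absence of a named term need no correlation.

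**Conclusion.** The concern holds as a gap in specification and reporting. The stated inputs give 20 per group (two-sided t-test) where the plan has 25, and power at 25 is 88.6% where the plan has 80%. This is a size and power that cannot be reproduced, with the discrepancy on the conservative side for that test. The weightier part is that the 80% is tied to no planned test. At 25 per group and a correlation of 0.3, two readings compatible with 7.2 differ by more than 17 points (80% for group-by-time, 97.5% for the post-treatment group effect), and at 0.7 their order reverses (99% and 93.0%). These powers rest on compound symmetry, SD 14 at each visit and a 12.8-point difference at both T1 and T2. Confidence is high that the derivation is incomplete and that the visible text names no deciding visit or term. It does not extend to any claim that 25 per group is too few. The point should be corrected before analysis, but it does not invalidate the design.

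**What to change.** - **In 4.2.1 and 7.2:** make the primary test the between-group difference in ODI at one post-treatment visit, T1 or T2 as the sponsor chooses, by ANCOVA adjusted for T0 ODI, two-sided 5%. Keep the repeated-measures ANOVA and the other visit as secondary.
- **In 7.1:** restate the calculation for that test. Give the visit, whether 14 is a score SD or a change SD, the sidedness, any loss allowance (25 recruited against the evaluable number) and the resulting power.

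Naming group-by-time as the deciding term would also remove the ambiguity and keep the planned method. At a correlation of 0.3, however, it has 80% power against 91% for ANCOVA at 25, and 70% against 84% at 20. A significant interaction also does not say at which visit the groups differ.

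With 20 evaluable per group, ANCOVA stays above 80% for correlations from 0.2 (82.0% if 14 is a score SD) to 0.9 (82.3% if it is a change SD). The margin is thin at the low end: with a score SD and correlation 0.2, 19 evaluable give 79.9%. The loss allowance should therefore be stated.

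The cost is a change of wording before the data are analysed. T0 ODI is already collected, and no patients, visits or measurements are added. The downside is that one of the two post-treatment visits becomes secondary.
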